7.3. Follow-Up Period

7.3.1. [REDACTED]

[REDACTED] procedures for all subjects are as follows:

- [REDACTED]
- Measure body weight and calculate BMI
- Perform physical exam and neurological exam
- Measure vital signs
- Record any concomitant medications
- Record any AEs
- Obtain blood samples for:
 - Chemistry, including ALP
 - Complete blood count and lymphocyte subsets
 - Total serum IgG and IgM, AMA and hsCRP

If the absolute peripheral lymphocyte count has not recovered to at least 80% of the baseline value, or reached normal ranges at the 2-week follow-up, the subject must return for weekly CBC tests until the absolute peripheral lymphocyte count has returned to at least these values.

8. DATA MANAGEMENT

8.1. Data Collection

All data (ECGs, clinical laboratory data, and all other study-related data) will be collected according to the sponsor/CRO's SOPs or according to study site standards, if applicable.

8.2. Data Coding

8.2.1. Adverse Events

AEs will be coded using the most current Medical Dictionary for Regulatory Activities (MedDRA) and tabulated, including categorical information of interest such as onset and resolution times, time of onset relative to dose, severity at onset, maximum severity, causal relationship to study medication, and action taken. Whenever possible, a constellation of signs and symptoms should be recorded as a unifying diagnosis (e.g., self-limited fever, runny nose, cough, and scratchy throat should be captured as an upper respiratory infection rather than by the individual signs and symptoms). AEs will be regarded as 'pre-treatment' if they occur between screening and the time of administration of the first dose of etrasimod. All other AEs that occur after the first dose of study medication will be considered to be 'treatment-emergent'.

8.2.2. Concomitant Medications and Non-Drug Treatments

Due to the variability in how medications are recorded, a standard naming convention is required to tabulate this data effectively. A common method of standardization is to categorize medications by their Preferred Term (PT). Medications will be coded using the World Health Organization Drug Dictionary (WHO DD), Format C.

8.2.3. Medical History

Medical history will be coded using the most current MedDRA-version.

9. PLANNED STATISTICAL METHODS

Summary statistics will be provided to describe efficacy and safety measures. Confidence interval of key efficacy measures will be also produced for non-inferential comparisons with historical data.

9.1. Hypotheses

There are no formal hypothesis tests specified in this open-label study due to the lack of a control treatment group.

9.2. Sample Size and Power Calculations

There is no formal sample size estimation for this proof-of-concept open label study. A sample size of 20 subjects is reasonable to assess the efficacy and safety of etrasimod in the target population.

9.3. Analysis Populations

Efficacy endpoints will be analyzed in enrolled patients who have baseline and at least one post-baseline measure.

Safety endpoints will be analyzed in enrolled patients who received at least one dose of the study drug.

9.4. Demographics and Baseline Characteristics

All baseline patient characteristics of demographic data (age, height, weight, race), disease history, medical history (abnormalities only), physical examination (abnormalities only), and concomitant medications at study entry will be listed for all patients.

Demographic data will be summarized and tabulated. Continuous variables will be summarized using number of observations (n), mean, standard deviation (SD), median, minimum, and maximum. Frequencies and percentages will be reported for all categorical data.

9.5. Efficacy Endpoints

- change from baseline to Week 12 and 24 in serum ALP concentration.
- change from baseline to Weeks 12 and 24 in:
 - Complete blood counts (including lymphocytes and subsets thereof).
 - hsCRP, ALT, AST, GGT, [REDACTED] C4 and [REDACTED] serum concentrations.
 - Total serum IgG, IgM, and AMA.
 - QoL, pruritus and fatigue (using the PBC-40 score and 5-D pruritus scales).
 - Ophthalmological examinations:
 - The Schirmer Test

9.6. Statistical Methods

9.6.1. Efficacy Analysis

There are no inferential comparisons for study endpoints. Summary statistical analyses will be performed for all efficacy measures. For proportion-based measures, N, frequencies, proportion and its 95% confidence interval (CI) will be produced. For continuous measure, N, mean, median, range, and SD will be produced for observed values, and additional 95% CI for change or percent change from baseline will be produced if applicable.

9.6.2. Subgroup Analyses

Exploratory analysis of main study endpoints will be performed in subset of patients of medical interests, such as patient demographics, baseline ALP levels, baseline disease characteristics, biomarker, previous disease treatment received, etc. [REDACTED]

9.6.3. Pharmacokinetic Analysis

Pharmacokinetic parameters of etrasimod, and its metabolites (if possible) will be calculated using non-compartmental methods. [REDACTED]

Individual etrasimod plasma concentrations at specified time points will be listed for each patient. Individual plasma concentration-time points of etrasimod will be plotted on both a linear and a semi-logarithmic scale for each dose level. [REDACTED]

9.6.4. Interim Analysis

An informal interim analysis of safety and efficacy will be performed when up to half the patients have finished 12 weeks of treatment.

9.7. Safety Analysis

Safety and tolerability will be assessed by a review of all safety parameters including AEs, laboratory safety parameters, [REDACTED] vital signs, and ECG. AEs will only be presented as summary tabulations. When assessing change from baseline, a baseline measurement is also required. Baseline for the safety analysis is defined as the average of the pre- dose measurements. No missing data will be imputed for the safety analysis. For continuous variables, summary statistics (N, mean [or median], SD, mean [or median] change/percent change) and 95% CI will be produced if applicable; for proportion-based measures, N, frequencies, proportion and its 95% CI will be produced.

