6.15.1. Adverse Event Reporting

Patients will be instructed to report all AEs, which can be reported at any time. AEs that occur from ICF signature until the time of administration of the first dose of etrasimod will be regarded as ‘pre-treatment’ and recorded as an AE. All events reported following study medication administration up to 30 days after the last medication intake will be presented as treatment emergent AEs (TEAEs).

Monitoring of ongoing AEs will be continued up to 30 days after study medication administration.

[figure not shown]
For this study, an AE is defined as: “Any untoward medical occurrence in a study patient administered etrasimod which does not necessarily have to have a causal relationship with this treatment.” An AE can therefore be any unfavorable and unintended sign (including an abnormal

laboratory finding), symptom, or disease temporally associated with the use of the study medication, whether or not related to the product. AEs can be any of the following:

- Unfavorable changes in general condition
- Subjective or objective signs/symptoms
- Concomitant disease or accidents
- Clinically relevant adverse changes in laboratory parameters observed in a patient in the course of a clinical study
- Pre-existing conditions which worsen in severity or frequency or which have new signs/symptoms associated with them

Lymphopenia will not be captured as an AE because it is an expected pharmacologic effect of the drug.

AEs will be elicited at the time indicated in the schedule. Any adverse or unexpected events, signs and symptoms will be fully recorded on the AE Form including details of intensity, onset, duration, outcome and relationship to the drug as determined by the PI. Whenever possible, a constellation of signs and symptoms should be recorded as a unifying diagnosis (e.g., self-limited fever, runny nose, cough, and scratchy throat should be captured as an upper respiratory infection rather than by the individual signs and symptoms). AEs may also be reported at any time. The type and duration of follow-up of patients after AEs will be documented.

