9.7.1. Adverse Events

AEs will be coded using the most current MedDRA and tabulated, including categorical information of interest such as onset and resolution times, time of onset relative to dose, severity at onset, maximum severity, causal relationship to study medication, and action taken. AEs will be regarded as 'pre-treatment' if they occur between screening and the time of administration of the first dose of etrasimod. All other AEs that occur after the first dose of study medication will be considered to be 'treatment-emergent'.

Pre-treatment and treatment-emergent AEs will be listed by patients, in terms of seriousness, severity and intensity (assessed according to the CTCAE v4.03; 14Jun2010 definitions³¹). TEAEs will be classified according to system organ class.

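### The no-imputation rule in 9.7 reaches AE onset, causality and grade, so incompletely recorded AEs could be lost from the treatment-emergent, related or severity counts

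*Combined protocol and SAP*

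**What the plan says.** Section 9.7 sets the scope of the safety analysis: "Safety and tolerability will be assessed by a review of all safety parameters including AEs, laboratory safety parameters", followed by vital signs and ECG. After a sentence on change from baseline ("When assessing change from baseline, a baseline measurement is also required") and one defining baseline, it states: "No missing data will be imputed for the safety analysis". No exception is given for AEs.

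Section 9.7.1 then classifies AEs by when they happen: "AEs will be regarded as 'pre-treatment' if they occur between screening and the time of administration of the first dose of etrasimod", and "All other AEs that occur after the first dose of study medication will be considered to be 'treatment-emergent". Section 8.2.1 uses the same definition. Both sections tabulate AEs by onset relative to dose, severity at onset, maximum severity and causal relationship.

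Section 6.15.1 defines the treatment-emergent group differently: "All events reported following study medication administration up to 30 days after the last medication intake will be presented as treatment emergent AEs (TEAEs". It also requires the AE form to be filled in completely, with "details of intensity, onset, duration, outcome and relationship to the drug as determined by the PI".

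Section 6.15.4 has two causality categories, related and not related. No section says how an incomplete onset date, a missing relationship or a missing grade is handled in the tables.

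**The concern.** Leaving a missing laboratory, ECG or vital-sign reading missing is reasonable. AE classification is different. Each AE table needs a yes or no on three questions: did the event start after first dose, is it related, and how severe was it. The usual practice is to prespecify a conservative answer when the record is incomplete. A rule against imputing anything forbids that answer and puts nothing in its place.

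The pre-treatment period is not empty. AEs are collected from consent (6.15), and screening runs 5 to 8 weeks before dosing (3.1), so the boundary at first dose matters. It is also a clock time, so an AE dated to Day 1 with no time recorded has the same problem as one dated only to the month.

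At stake are the treatment-emergent, related and severity counts, in a study whose sole primary objective is safety and tolerability (2.1). If an incompletely recorded event is left out, the numerator falls and the safety population in the denominator does not. Any loss therefore runs towards under-reporting.

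**Working it through.** The plan states no AE rate, no missing-data rate and no formal sample size, so there is no figure of its own to reproduce. The check is of wording, with two illustrations of size.

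**Which count each missing item touches**

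| Missing item | Overall TEAE count | Related count | Severity count |
|---|---|---|---|
| Onset not placeable around first dose | At risk under 8.2.1 and 9.7.1; kept under 6.15.1 if reported after dosing | Follows the TEAE decision | Follows the TEAE decision |
| Causality | Not affected | At risk: fits neither category in 6.15.4 | Not affected |
| Grade | Not affected | Not affected | At risk |

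**The two TEAE definitions**

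- 8.2.1 and 9.7.1 turn on occurrence after first dose and give no end of window.
- 6.15.1 turns on reporting after dosing, up to 30 days after last intake.
- 6.15.1 defines pre-treatment events by occurrence. An event that began before dosing and was reported afterwards therefore meets both of its own definitions.

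**How often a month-only date is ambiguous**

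Inputs: screening of 35 or 56 days (5 or 8 weeks, 3.1), 24 × 7 = 168 treatment days, and 30 days after last dose (6.15.1). Assumption: AE onset is uniform over the window, averaged over calendar dates for Day 1.

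1. Total AE window: 35 + 168 + 30 = 233 days, or 56 + 168 + 30 = 254 days.
2. Without imputation, a month-only date is ambiguous about first dose only in the calendar month of Day 1, on average about 365/12 = 30.4 days.
3. Share of the window: 30.4/233 = 13%, or 30.4/254 = 12%.
4. On-drug part only: 168 + 30 = 198 days. On average about 15 of these fall in the Day 1 month (range 0 to 30), so 15/198 = 7.6% (range 0 to 15.2%).

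These shares apply only to AEs whose date is known to the month. The documents do not say how many there would be.

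**What one patient is worth**

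Taking N = 20 (9.2; the synopsis says up to 20), one patient is 1/20 = 5 percentage points. Exact (Clopper-Pearson) 95% intervals:

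| Patients with event | Proportion | 95% CI |
|---|---|---|
| 0/20 | 0% | 0 to 16.8% |
| 1/20 | 5% | 0.1 to 24.9% |
| 3/20 | 15% | 3.2 to 37.9% |
| 4/20 | 20% | 5.7 to 43.7% |

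Losing one patient from a count moves 4/20 to 3/20 or, at the extreme, 1/20 to 0/20. It moves patient-level incidence only if that patient has no other qualifying event.

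**The case against.** The strongest reply is that the plan never says incomplete AEs are excluded. A reader might infer from 9.7 that such events must drop out of the tables. That is not in the documents: they bar imputation and are otherwise silent, so loss is a possible consequence of an undefined step. This part of the objection stands, and the point is worded accordingly.

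It also stands that 6.15.1 would keep an undated event reported on treatment, and that most month-only dates can be placed from the known part. A further inference, that a year-only date leaves the whole window ambiguous, fails in general. With first dose on 1 September, the 198-day window runs into March, and an event dated to the following year is plainly after first dose.

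Three other replies carry less weight.

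- **The rule may be meant for measured values.** It follows two sentences about baseline, so that reading is open. The wording does not limit it, and AEs are named at the start of the same section.
- **Collection rules make gaps unlikely.** 6.15.1 asks for full recording, 6.15.3 for severity at onset and maximum severity, AEs are recorded at visits before and after first dose, and case report forms are monitored (11.3). This lowers the likely number of gaps, but a missing-data rule exists for the records where collection fails.
- **Listings show everything.** 9.7.1 does list AEs by patient, but 9.7 says AEs appear only in summary tables, so the safeguard is itself in doubt. The listing in 9.7.1 also refers to the same pre-treatment and treatment-emergent groups.

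The study is descriptive and has no hypothesis tests (9.1), which limits the consequences. It does not remove them, because descriptive AE rates are the primary result.

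**Conclusion.** The concern holds in limited form. On its wording, 9.7 forbids imputing AE onset, causality and grade, and nothing else in the plan says how such records are counted. An AE that cannot be placed around first dose could be lost from the treatment-emergent count under 8.2.1 and 9.7.1, with 6.15.1 pointing the other way. Missing causality or grade puts only the related or severity counts at risk.

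The direction is clear: any loss lowers the reported rates. The size is not. One patient is 5 points at N = 20. A month-only date would be ambiguous for about 12 to 13% of the AE window if onset is uniform. The number of AEs with incomplete records cannot be derived from the documents. This is a cheap improvement to the plan; there is no evidence that the safety results would be materially wrong.

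**What to change.** 1. In 9.7, limit the no-imputation sentence to laboratory, vital-sign and ECG values.
2. For the AE summaries only, add these conventions:
   - An AE with an incomplete onset date or time is treatment-emergent unless the known part of the onset date, or the stop date, shows that it began before first dose.
   - A missing relationship is counted as related.
   - A missing grade is shown in its own 'missing' row, with a conservative sensitivity count alongside.
   - The original missing values are shown in the listings.
3. Reconcile the TEAE definition in 6.15.1 (reported, up to 30 days after last intake) with 8.2.1 and 9.7.1 (occurring after first dose, no end of window), so that one rule appears in all three places.
4. Make no change to the trigger in 6.19. It governs live safety review, and these conventions are for the analysis tables.

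The cost is a few sentences and no new data collection. The downside is that reported TEAE or related rates may rise slightly.

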9.7.1. Adverse Events

AEs will be coded using the most current MedDRA and tabulated, including categorical information of interest such as onset and resolution times, time of onset relative to dose, severity at onset, maximum severity, causal relationship to study medication, and action taken. AEs will be regarded as 'pre-treatment' if they occur between screening and the time of administration of the first dose of etrasimod. All other AEs that occur after the first dose of study medication will be considered to be 'treatment-emergent'.

Pre-treatment and treatment-emergent AEs will be listed by patients, in terms of seriousness, severity and intensity (assessed according to the CTCAE v4.03; 14Jun2010 definitions³¹). TEAEs will be classified according to system organ class.

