6.15.3. Assessment of Adverse Event Severity

The severity of each AE will be assessed at onset by a nurse and/or physician. When recording the outcome of the AE the maximum severity of the AE experienced will also be recorded. The severity of the AE will be graded according to the CTCAE v4.03³¹ definitions, listed below:

Grade 1: Mild; asymptomatic or mild symptoms; clinical or diagnostic observations only; intervention not indicated.

Grade 2: Moderate; minimal, local or noninvasive intervention indicated; limiting age-appropriate instrumental Activities of Daily Living (ADL)*.

Grade 3: Severe or medically significant but not immediately life-threatening; hospitalization or prolongation of hospitalization indicated; disabling; limiting self-care ADL**.

Grade 4: Life-threatening consequences; urgent intervention indicated.

Grade 5: Death related to AE.

Activities of Daily Living:

*Instrumental ADL refer to preparing meals, shopping for groceries or clothes, using the telephone, managing money, etc.

**Self-care ADL refer to bathing, dressing and undressing, feeding self, using the toilet, taking medications, and not bedridden.

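### The adverse event split by timing alone can leave a screening-onset event that worsens on etrasimod out of the treatment-emergent table

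*Combined protocol and SAP*

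**What the plan says.** The analysis rule is in Section 9.7.1 and is repeated in Section 8.2.1. AEs are pre-treatment "if they occur between screening and the time of administration of the first dose of etrasimod". For the rest, "All other AEs that occur after the first dose of study medication will be considered to be" treatment-emergent. Both sentences turn on when the event occurs, and neither mentions worsening.

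Section 6.15.3 sets out how severity is captured: "The severity of each AE will be assessed at onset by a nurse and/or physician", and then "When recording the outcome of the AE the maximum severity of the AE experienced will also be recorded". Section 9.7.1 tabulates both, listing "severity at onset, maximum severity, causal relationship to study medication, and action taken" among the items of interest. No grade at the time of first dose is requested.

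Section 6.15.1 gives its own version of the split. "AEs that occur from ICF signature until the time of administration of the first dose of etrasimod will be regarded as" pre-treatment, but "All events reported following study medication administration up to 30 days after the last medication intake will be presented as treatment emergent AEs (TEAEs"). The same section includes among the things an AE can be: "Pre-existing conditions which worsen in severity or frequency or which have new signs/symptoms associated with them".

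AEs are collected from consent (Section 6.15), so the collection period includes the whole of the 5 to 8 week screening period.

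**The concern.** A TEAE table is meant to show what appeared or got worse on drug. A rule that looks only at the time of occurrence covers the first and is silent on the second. If a screening-onset AE is kept as a single record, its onset date places it before the first dose while its maximum grade may have been reached on etrasimod. Such an event would sit in the pre-treatment group with an on-drug severity.

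Safety and tolerability is the only primary objective (Section 2.1). There is no control arm and no hypothesis test (Section 9.1), so descriptive safety summaries carry the conclusion, and the TEAE table is a central one. Two people who both follow the text, one at a site and one programming tables, could classify the same event differently.

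**Working it through.** The plan gives no figure that depends on this rule, so the check is a comparison of the sections, followed by a note on scale.

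**Step 1. Apply each rule to the possible cases.**

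| Case | Sections 8.2.1 and 9.7.1 | Section 6.15.1 |
|---|---|---|
| A. Symptom present before consent, worsens on drug | First becomes an AE after first dose: treatment-emergent | Worsening is an AE, reported after dosing: treatment-emergent |
| B. AE starts and resolves in screening | Pre-treatment | Pre-treatment |
| C. AE starts in screening, ongoing on Day 1, no worsening | Pre-treatment | Pre-treatment |
| D. AE starts in screening, ongoing on Day 1, worsens on drug | Pre-treatment if kept as one record; treatment-emergent if the worsening is entered as a new AE | Pre-treatment by occurrence; treatment-emergent if the worsening is an event reported after dosing |
| E. AE starts on treatment | Treatment-emergent | Treatment-emergent |

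Only case D is unsettled. In Sections 8.2.1 and 9.7.1 the answer depends on a record-keeping rule that the documents do not state. Section 6.15.1 sorts its first group by when events occur and its second by when they are reported, so a case D event can meet both descriptions.

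**Step 2. Can the analyst recover the answer from the severity fields in Section 6.15.3?** Take two hypothetical patients, each with an AE that is Grade 1 at onset in screening.

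- Patient 1 rises to Grade 3 before Day 1 and does not worsen on drug.
- Patient 2 is still Grade 1 on Day 1 and rises to Grade 3 on drug.

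On the two severity items requested, both records read onset Grade 1, maximum Grade 3. The first is not treatment-emergent on any reading; the second should be. Grade at first dose would separate them, and it is not requested. The eCRF itself is not among the documents, so it may hold more than Section 6.15.3 asks for.

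**Step 3. Scale.** Section 9.2 gives 20 patients. Assume all 20 are treated. One patient reclassified in a given table row changes that row by 1/20 = 5 percentage points, provided the patient has no other event in the row; otherwise the change is 0. Section 9.7 calls for 95% confidence intervals on proportions without naming a method. Assuming exact (Clopper-Pearson) intervals:

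- 0/20: 0% to 1 − 0.025^(1/20) = 16.8%
- 1/20 (5%): 0.1% to 24.9%

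**Step 4. Number affected.** This would be 20 × (share with a screening-onset AE ongoing on Day 1) × (share of those that worsen on drug). The documents give neither share, so the product cannot be evaluated.

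**The case against.** The strongest answer is Section 6.15.1. It makes worsening of an existing condition an AE in its own right and presents whatever is reported after dosing, within the 30-day window, as a TEAE. Read together, those sentences put an on-drug worsening in the TEAE table. That one record runs across the first dose is an inference from Section 6.15.3, not something it states. This stands as far as it goes: misclassification is possible under the text, not dictated by it. It does not close the gap. The worsening item defines what an AE can be, without saying whether an AE already on record gets a second entry, and the analysis sections carry no matching clause.

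A reader might also infer that many patients are affected, because Section 1.1 reports fatigue in nearly 80% and pruritus in 20-70% of patients with PBC. The documents do not support that step. Symptoms already present before consent fall under case A, which both rules treat as treatment-emergent when they worsen. Only AEs that newly begin in screening are exposed. Pruritus and fatigue are also measured separately as change from baseline on the 5-D and PBC-40 scales (Section 9.5).

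Nor does the event vanish. Section 9.7.1 lists pre-treatment and treatment-emergent AEs by patient with severity, and with up to 20 patients a raised maximum grade would be seen. (Section 9.7 says AEs appear only as summary tables; I take the more specific Section 9.7.1 to govern.) The committee-review trigger in Section 6.19 counts patients with Grade 3 or higher events without limiting them to TEAEs, so on its wording it is unaffected. These points stand and limit the consequence to the TEAE summary tables.

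**Conclusion.** The gap is real but narrow. Sections 8.2.1 and 9.7.1 split AEs by timing alone, and an AE that newly starts in screening, is ongoing on Day 1 and worsens on etrasimod can be left out of the TEAE table by someone following them as written. If it is kept as one record, the error runs in one direction, towards fewer TEAEs.

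A reader might infer that every such event will be tabulated as pre-treatment, or that the plan as a whole can only hide on-drug worsening. Section 6.15.1 supports the opposite classification, so neither inference holds; the documents leave the matter open.

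The size is at most 5 percentage points per patient in any one row, assuming 20 treated patients and no other event for that patient in the row. The number of such patients cannot be estimated from the documents. The point is worth correcting because it touches the sole primary objective, the change is cheap, and the grade at first dose cannot be reliably reconstructed later if it is not captured at the time.

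**What to change.** In Sections 8.2.1 and 9.7.1, define a TEAE as an AE with onset after the first dose, or an AE present before the first dose that increases in CTCAE grade or becomes serious after it. Reword Section 6.15.1 so that it gives the same definition and uses the same basis, occurrence or report, for both groups.

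In Section 6.15.3 and the eCRF instructions, choose one recording method: either record the grade at first dose for every AE ongoing on Day 1, or open a new record when the grade rises after the first dose. Settle this before data are collected.

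The cost is a few sentences of text and one eCRF field or instruction, with no added visits or samples. The downside is that TEAE rates may read slightly higher.
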